1.0 Research Introduction

1.1 Purpose/Specific Aims

The goal of the study is to determine whether a high-dose corticosteroid regimen in patients admitted to the hospital with COPD exacerbations is associated with better clinical outcomes and at acceptable risk of adverse effects compared to a low-dose corticosteroid regimen. The study population includes patients ≥ 40 years-old with a ≥ 10 pack-years smoking history and a diagnosis of COPD, emphysema, or chronic bronchitis who present to the emergency room with increased dyspnea, increased sputum, or increased cough that requires admission to the hospital. We will perform a prospective, randomized, double-blinded study to determine if a high-dose corticosteroid regimen, which is already in use in clinical practice, decreases treatment failure compared to a low-dose corticosteroid regimen that is based on national consensus guidelines.

A. Objectives

Primary Aim: To determine if a high-dose corticosteroid regimen is associated with decreased rates of treatment failure compared to a low-dose corticosteroid regimen.

Secondary Aims:

- a) To determine if a high-dose corticosteroid regimen is associated with a reduced length of stay.
- b) To determine if a high-dose corticosteroid regimen is associated with better quality of life scores.

Tertiary Aim: To determine if a high-dose corticosteroid regimen is associated with an increased risk of short-term adverse effects.

B. Hypotheses / Research Question(s)

Protocol Number:

PI Name: [name]

Protocol Title: Determining Optimal Dose of
Corticosteroids in COPD Exacerbations: A
Pilot Study

3

RESERVED FOR IRB STAMP
DO NOT MODIFY THIS SPACE

IRB Form Version v120116

Our hypothesis is that high-dose corticosteroids are associated with a decreased rate of treatment failure, shorter length of hospital stay, and improved quality of life with similar risk of adverse effects.

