1.3 Research Design and Methods

We will perform a pilot study evaluating two commonly used doses of corticosteroids in the treatment of acute exacerbation of COPD. The study design is a randomized, double-blinded, prospective interventional trial. Our research staff will recruit, consent, and enroll patients admitted to the hospital with a diagnosis of COPD exacerbation. We will create randomization tables that will be provided to the research pharmacist. The research pharmacist will be telephoned, and they will randomly assign the patient to a low-dose or high-dose corticosteroid regimen. Medication will be prepared by a research pharmacist to maintain blinding. For in-hospital intravenous medication, the research pharmacist will provide to the nurses a container with the patient's name and medication without the dose. For oral medication, the pills will be inserted into a capsule and provided to nurses for in-hospital administration. At the time of discharge, a container filled with the remaining oral medication will be provided to the patient. Subjects receiving intravenous corticosteroid may be discharged to a nursing home before completion of the IV component of the regimen. Their regimen will be converted to oral equivalents, and a container will be provided to the nursing home. Copies of the patient brochure, signed consent, and written discharge instructions will also be provided. All data will be collected by our research staff via chart review of index and subsequent hospitalizations within the 30-day follow up period, as well as a phone interview with the patient at 30-days. The Clinical COPD Questionnaire will be administered during the phone interview. A patient is considered lost to follow-up if the data collection is not collected within 14 days after the 30-day follow-up date. In the event that we are unable to contact the patient, we will telephone the participant's personal medical doctor to confirm the patient's status. If necessary, we will obtain medical records for any outpatient physician visits made during the 30-day follow up period.

- i. Primary Outcome: The composite of treatment failure defined as death, intubation, re-admission for COPD exacerbation, or intensification of therapy (increased steroid use, change of antibiotic therapy) within a 30-day follow-up period.

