- ii. Secondary Outcomes: Length of hospital stay and quality of life measured by Clinical COPD Questionnaire. The CCQ consists of 10 questions about the severity of COPD symptoms and limitation of activities over the prior week.
- iii. Tertiary Outcome: Composite outcome of short-term adverse effects. Defined as hyperglycemia, hypertension, adrenal suppression, psychiatric disturbance, infection, and gastrointestinal bleed that require a consultation, an invasive procedure, or initiation of a specific therapy.

Protocol Number:

PI Name: [name]

Protocol Title: Determining Optimal Dose of
Corticosteroids in COPD Exacerbations: A
Pilot Study

5

RESERVED FOR IRB STAMP
DO NOT MODIFY THIS SPACE

IRB Form Version v120116

Subject participation in the study ends after the 30 day follow up period. Study staff will also maintain contact with the patient's hospital physician and actively review the patient's chart during the index hospitalization for safety and adverse effect monitoring. Please see the study data collection form for additional specific data points that will be collected.

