1.6 Study Variables

A. Independent Variables, Interventions, or Predictor Variables

Our independent variable is the corticosteroid intervention. We chose to compare two commonly used corticosteroid regimens for COPD exacerbation that vary by dosage strength but not duration. Both of these regimens may be considered "standard of care."

B. Dependent Variables or Outcome Measures

- i. Primary Outcome: The composite of treatment failure defined as death, intubation, re-admission for COPD exacerbation, or intensification of therapy (increased steroid use, change of antibiotic therapy) within a 30-day follow-up period.
- ii. Secondary Outcomes: Length of hospital stay and quality of life measured by Clinical COPD Questionnaire. The CCQ consists of 10 questions about the severity of COPD symptoms and limitation of activities over the prior week.
- iii. Tertiary Outcome: Composite outcome of short-term adverse effects. Defined as hyperglycemia, hypertension, adrenal suppression, psychiatric disturbance, infection, and gastrointestinal bleed that require a consultation, an invasive procedure, or initiation of a specific therapy.

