1.9 Interviews, Focus Groups, or Surveys

A. Administration

The Clinical COPD Questionnaire (CCQ) will be administered by research staff during a telephone interview at 30 days following subject enrollment into the study. The patient will be provided this document in advance, at the time of hospital discharge, for reference.

B. Study Instruments

The CCQ is a validated tool utilized in prior literature to assess quality of life in patients with COPD. Higher scores indicate increased severity of symptoms and/or poorer quality of life, and are associated with increased mortality. ^{17, 18, 19, 20, 21}

In addition to the CCQ, research staff will query the patient about study endpoints during the follow-up telephone interview (re-admission, changes to steroid regimen, antibiotic therapy, and steroid-associated adverse effects that require a consultation, an invasive procedure, or initiation of a specific therapy).

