4.2 Subject Selection and Enrollment Considerations

A. Recruitment Details

Emergency room and medical staff will be informed about the study objectives, eligibility criteria, and protocol requirements prior to the initiation of the study. We will only recruit patients of physicians who are willing to follow the study protocol. Study staff will be notified of potential subjects that are identified by the emergency room staff and physicians. Study staff can also access a list of patients in the hospital who are being treated with prednisone or methylprednisolone to identify additional potential study subjects. Study staff will assess the medical records of each of the potential study subjects and, if they meet all eligibility criteria, approach the patient for consent. Eligible patients would have a diagnosis of COPD, emphysema, or chronic bronchitis with a presentation of increased dyspnea, increased sputum, or increased cough.

B. Source of Subjects

Subjects will be recruited from the RWJUH emergency room and general medical ward.

C. Method to Identify Potential Subjects

See section A above.

D. Subject Screening

Individuals will be screened for study inclusion by study staff using the eligibility and screening form.

▪ Inclusion Criteria

- Patients with a diagnosis of COPD, emphysema, or chronic bronchitis
- Age \geq 40 years-old
- Smoking history \geq 10 pack-years
- Presentation to the emergency room with increased dyspnea, increased sputum, or increased cough
- Admission to the hospital

▪ Exclusion Criteria

- Alternative diagnosis for cause of dyspnea, increased sputum or cough
- Patients who require intubation at time of recruitment
- Patients who are unable to give consent
- Patients who are pregnant or could be pregnant or are currently breast-feeding

Protocol Number:

PI Name: [name]

Protocol Title: Determining Optimal Dose of
Corticosteroids in COPD Exacerbations: A
Pilot Study

9

RESERVED FOR IRB STAMP
DO NOT MODIFY THIS SPACE

IRB Form Version v120116

- Women of child-bearing age who cannot use methods of contraception as described in the consent, including condoms, female condoms, cervical caps, diaphragms, and IUDs.
- Patients who were previously entered into the trial and are re-admitted to the hospital with a new COPD exacerbation.

A younger population is excluded because COPD is primarily an adult disease.

E. Recruitment Materials

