4.9 Risks to Subjects

A. Description of Subject Risk

Patients entered into this study would have received corticosteroids regardless of study participation. The optimal dose of corticosteroids in the treatment of COPD exacerbations in patients admitted to the hospital is unknown. The proposed regimen for the low-dose

Protocol Number:

12

PI Name: [name]

Protocol Title: Determining Optimal Dose of
 Corticosteroids in COPD Exacerbations: A
 Pilot Study

*RESERVED FOR IRB STAMP
 DO NOT MODIFY THIS SPACE*

IRB Form Version v120116

corticosteroid group is based on national consensus guidelines, and the regimen for the high-dose group, on current clinical practices. Thus, the risks to subjects from study participation are comparable to current standard of care. Any patient who does not clinically improve appropriately can have their regimen intensified based on the clinical judgement of his/her physician. Additionally, if the treating physician feels that the patient is experiencing undue adverse effects from study corticosteroid, the patient may be withdrawn from the study at any time. Minor side effects (ie. hyperglycemia) from short-term systemic corticosteroids are common and generally limited in duration to the duration of treatment. They are an accepted consequence of the standard of care for COPD exacerbation. Major adverse effects are uncommon.

B. Procedures for Risks to Embryo, Fetus, and/or Pregnant Subjects

N/A, these subjects are excluded from the study.

C. Risks to Non-Subjects

N/A

D. Assessment of Social Behavior Considerations

Temporary psychiatric symptoms or exacerbation of pre-existing psychiatric disease are uncommon but potential side effects of corticosteroid therapy. The duration of these side effects are limited to the duration of corticosteroid therapy. Patients entered into this study would have received corticosteroids regardless of study participation. Thus, study participation is unlikely to increase risk of these side effects.

▪ **Reasonably Foreseeable Risks**

There are no other reasonably foreseeable social behavior risks of participation in this study.

▪ **Risk Of Imposing An Intervention On Subject With Existing Condition**

See above.

▪ **Other Foreseeable Risks**

N/A

▪ **Observation And Sensitive Information**

N/A

E. Minimizing Risks

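### The adverse-effect composite does not count a dose increase of an existing drug, so worsening hyperglycemia or hypertension in already-treated patients may be missed or scored inconsistently

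*Combined protocol and SAP*

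**What the plan says.** Section 1.3 makes short-term adverse effects a composite tertiary outcome: "Defined as hyperglycemia, hypertension, adrenal suppression, psychiatric disturbance, infection, and gastrointestinal bleed", limited to those "that require a consultation, an invasive procedure, or initiation of a specific therapy". Section 1.6 repeats the definition. Section 1.9 applies the same threshold to the 30-day telephone interview, asking about "steroid-associated adverse effects that require a consultation, an invasive procedure, or initiation of a specific therapy".

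There are thus three alternative routes to an event. None names an increase in existing treatment. The term for the qualifying therapy is not defined, and no rule covers patients who arrive already taking glucose-lowering or antihypertensive drugs.

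For the primary outcome the same sections do count escalation: "intensification of therapy (increased steroid use, change of antibiotic therapy".

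The eligibility criteria in section 4.2 require age 40 or over and at least 10 pack-years. Diabetes, hypertension and their treatment are not among the exclusions. Section 4.9 states that "Minor side effects (ie. hyperglycemia) from short-term systemic corticosteroids are common" but gives no rate.

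Section 6.1 plans both absolute differences and relative risks with 95% confidence intervals. Section 1.5 gives the purpose of the 125-patient pilot as finding the outcome rates, so that a later trial can be sized. Sections 1.3 and 6.3 refer to a data collection form for further data points and for predefined adverse effects; that form is not among the documents.

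**The concern.** Consider two patients with the same steroid-induced rise in glucose. One has never been treated and receives a first dose of insulin: an event. The other takes insulin at home and has the dose raised by the ward team without a consultation: not an event on a plain reading. The same contrast arises for blood pressure. A third patient, on tablets, who is given insulin for the first time could be scored either way, because it is not stated whether an added agent is an initiation.

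Two things are at stake. First, the event rates are a main product of this pilot, and they would be too low by an unknown amount. Second, the trial hypothesizes "improved quality of life with similar risk of adverse effects". If high-dose treatment also raises harm in already-treated patients, leaving out their events narrows the absolute difference, in the direction of that hypothesis.

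**Working it through.** The plan states no adverse-effect rate, effect size or power, so there is no figure to reproduce. All rates and shares below are assumptions, used only to show direction and range.

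**Illustration 1: the dose effect is present in treated patients.**

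Assume that a share f of patients is already treated. Assumed true event rates (low vs high dose) are 40% vs 60% in them and 15% vs 30% in the rest. Let c be the fraction of treated patients' events that still count, through a consultation or a new drug read as initiation. The counted rate in an arm is

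f × c × (treated rate) + (1 − f) × (untreated rate).

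For f = 0.3 and full counting:
- low dose: 0.3 × 0.40 + 0.7 × 0.15 = 22.5%
- high dose: 0.3 × 0.60 + 0.7 × 0.30 = 39.0%
- difference 16.5 points, relative risk 39.0/22.5 = 1.73

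| f | c | Low vs high (%) | Difference (points) | Relative risk |
|---|---|---|---|---|
| 0.2 | 1 | 20.0 vs 36.0 | 16.0 | 1.80 |
| 0.2 | 0.8 | 18.4 vs 33.6 | 15.2 | 1.83 |
| 0.2 | 0.5 | 16.0 vs 30.0 | 14.0 | 1.88 |
| 0.2 | 0 | 12.0 vs 24.0 | 12.0 | 2.00 |
| 0.3 | 1 | 22.5 vs 39.0 | 16.5 | 1.73 |
| 0.3 | 0.8 | 20.1 vs 35.4 | 15.3 | 1.76 |
| 0.3 | 0.5 | 16.5 vs 30.0 | 13.5 | 1.82 |
| 0.3 | 0 | 10.5 vs 21.0 | 10.5 | 2.00 |
| 0.4 | 1 | 25.0 vs 42.0 | 17.0 | 1.68 |
| 0.4 | 0.8 | 21.8 vs 37.2 | 15.4 | 1.71 |
| 0.4 | 0.5 | 17.0 vs 30.0 | 13.0 | 1.76 |
| 0.4 | 0 | 9.0 vs 18.0 | 9.0 | 2.00 |

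Both event rates and the absolute difference fall as fewer events are captured. The relative risk rises, because the assumed relative effect is smaller in treated patients (60/40 = 1.5) than in the rest (30/15 = 2.0).

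**Illustration 2: the same fraction of events lost in both arms.**

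Let s be the share of all would-be events that fall in treated patients, equal in both arms. Each rate is multiplied by 1 − s(1 − c). With assumed full rates of 20% vs 35% (15 points, relative risk 1.75), s = 0.4 and c = 0, the factor is 0.6. The counted rates are 12% vs 21%: 9 points, relative risk still 1.75. Over s = 0.2 to 0.6 and c = 0 to 0.8 the factor runs from 0.40 to 0.96, and the difference from 6.0 to 14.4 points. If other components unrelated to dose add 5% independently in each arm, the relative risk does fall slightly, from 1.59 to 1.52 at s = 0.4, c = 0.

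**Illustration 3: no dose effect in treated patients.**

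Assume 40% of patients treated, with 30% events in both arms, and 10% vs 25% in the rest.
- Full count: 0.4 × 30 + 0.6 × 10 = 18% vs 0.4 × 30 + 0.6 × 25 = 27%; difference 9 points, relative risk 1.50.
- Treated patients' events dropped: 6% vs 15%; difference still 9 points, relative risk 2.50.

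**What is common to all three.** The event rates are understated whenever c is below 1. The absolute difference shrinks in the first two illustrations and is unchanged in the third. The relative risk can rise, stay level or fall.

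**Planning consequence.** With the rates of illustration 1 at f = 0.3, the sample size per arm for 80% power on harm (two-sided 0.05, normal approximation) is 122 on the full count, 153 at c = 0.5 and 188 at c = 0.

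**The case against.** Several points on the other side stand.

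- **Initiation is one of three routes.** A reader might infer that only initiation counts. The text does not say that: a consultation or an invasive procedure also qualifies, and an added drug can reasonably be read as an initiation. What is clearly left out is a pure dose increase with neither of the other two.
- **Events need not be largely lost.** A reader might infer that most worsening in treated patients goes uncounted. No figure in the documents supports this. At 80% capture the first illustration gives 15.2 to 15.4 points against 16 to 17, a slight effect.
- **The bias is not toward no effect on every scale.** A reader might infer that the harm comparison as a whole is pulled toward the null. Section 6.1 plans relative risks too, and in the first and third illustrations these move away from 1.
- **Loss of power matters little.** Sections 1.5 and 6.3 say that the pilot is not powered for its hypothesis or for safety, and section 6.1 assigns no alpha expressly to the tertiary composite.
- **Requiring a new intervention is a recognizable severity threshold.** Section 4.9 treats hyperglycemia as a minor, accepted effect, and only two of the six components are clearly affected.
- **The data collection form may settle the rule.**

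None of this closes the gap. A severity threshold should apply alike to treated and untreated patients, and this one does not. Disclaiming power does not help with rates that the pilot is meant to supply. If the form holds a rule, the outcome definition should state it.

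**Conclusion.** The point holds in a limited form. As worded, a dose increase of an existing glucose-lowering or antihypertensive drug, without a consultation or procedure, is not an adverse-effect event, and the status of an added agent is open. Worsening in already-treated patients may therefore be missed, or scored differently by different staff. The consequence that follows whenever such events occur and are missed is an understated harm rate. Shrinkage of the absolute difference follows if the dose effect also operates in treated patients; no general statement can be made about the relative risk.

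The size cannot be fixed from the documents. In the first illustration (20 to 40% of patients treated, 0 to 80% of their events captured), a difference of 16 to 17 points is recorded as 9.0 to 15.4. These are assumed rates, not estimates for this trial. The change is worth making because it is cheap and best settled before outcomes are scored, not because a large bias has been shown.

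**What to change.** In sections 1.3, 1.6 and 1.9, replace the third route with: initiation or escalation (dose increase or added agent over the pre-admission regimen) of a specific therapy. Word the 30-day telephone questions to match. Record pre-admission treatment for diabetes and hypertension from the chart, if the data collection form does not already do so. In section 6.1, add the initiation-only composite as a sensitivity analysis, and report the composite by baseline treatment status.

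This changes how outcomes are scored, not how patients are treated. It costs one phrase in three places and at most one further item in a chart review that is already planned. The downside is that escalation is somewhat more subjective than initiation and may bring in milder events. Research staff are not told the treatment arm (section 4.3), so scoring is blind, and the sensitivity analysis shows how far the result depends on the wider definition.

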1.4 Preliminary Data

No relevant preliminary data exists in our study. Interim analysis will not be performed on the data because of the relatively small sample size of this pilot study.

1.5 Sample Size Justification

This is a pilot study of 125 subjects to determine the rates of the outcomes so an adequate sample size can be determined and feasibility established. We do not anticipate including enough patients to have adequate power to definitively answer the hypothesis.

1.6 Study Variables

A. Independent Variables, Interventions, or Predictor Variables

Our independent variable is the corticosteroid intervention. We chose to compare two commonly used corticosteroid regimens for COPD exacerbation that vary by dosage strength but not duration. Both of these regimens may be considered "standard of care."

B. Dependent Variables or Outcome Measures

- i. Primary Outcome: The composite of treatment failure defined as death, intubation, re-admission for COPD exacerbation, or intensification of therapy (increased steroid use, change of antibiotic therapy) within a 30-day follow-up period.
- ii. Secondary Outcomes: Length of hospital stay and quality of life measured by Clinical COPD Questionnaire. The CCQ consists of 10 questions about the severity of COPD symptoms and limitation of activities over the prior week.
- iii. Tertiary Outcome: Composite outcome of short-term adverse effects. Defined as hyperglycemia, hypertension, adrenal suppression, psychiatric disturbance, infection, and gastrointestinal bleed that require a consultation, an invasive procedure, or initiation of a specific therapy.

1.7 Drugs/Devices/Biologics

We chose to compare two commonly used corticosteroid regimens for COPD exacerbations, both of which might be considered "standard of care." All corticosteroids will be prepared, stored, and dispensed at the RWJUH main pharmacy by the staff research pharmacist.

Protocol Number:

PI Name: [name]

Protocol Title: Determining Optimal Dose of
Corticosteroids in COPD Exacerbations: A
Pilot Study

6

*RESERVED FOR IRB STAMP
DO NOT MODIFY THIS SPACE*

IRB Form Version v120116

- i. Low dose arm: Methylprednisolone 10 mg IV q8hrs for 3 days*, then prednisone 40 mg PO daily for 4 days, then prednisone 30 mg daily for 1 day, then prednisone 20 mg daily for 1 day, then prednisone 10 mg daily x 1 day, then stop.

* If the patient is unable to receive IV medications, every three consecutive doses of methylprednisolone will be replaced with a single dose of prednisone 40 mg PO given daily.

- ii. High dose arm: Methylprednisolone 40 mg IV q8hrs for 3 days*, then prednisone 80 mg PO daily for 4 days, then prednisone 60 mg daily for 1 day, then prednisone 40 mg daily for 1 day, then prednisone 20 mg daily for 1 day, then stop.

* If the patient is unable to receive IV medications, every three consecutive doses of methylprednisolone will be replaced with a single dose of prednisone 80 mg PO given daily.

If patients in either group are discharged prior to day 4, IV methylprednisolone will be converted to PO as above.

